3.6.3 European Quality of Life-5 Dimensions (EQ-5D-5L)

The EQ-5D-5L will be analysed separately and not form part of this SAP.

CCI

3.6.6 Healthcare resource utilization

At randomization, retrospective BP-related healthcare resource utilization information will be collected with a one-year recall period. At all subsequent visits (see CSP Table 2), BP-related healthcare resource utilization information will be collected with a recall period of ‘since last scheduled visit’.

The data collected may be used to conduct exploratory economic analyses and include:

- Number and duration of medical care encounters, including surgeries, and other selected procedures (inpatient and outpatient);
- Duration of hospitalization (total days or length of stay, including duration by wards [eg, intensive care unit]);
- Outpatient medical encounters and interventions (including specialist visits, General Practitioner visits, home health care visits, and emergency room visits, etc.);
- Number and type of diagnostic and therapeutic tests and procedures.

Note: Cases of hospitalization occurring after signing of the ICF must be reported as an SAE (CSP Section 8.3).

All available data will be included, regardless of taking rescue medication or withdrawal from study.

Healthcare resource utilisation will be summarized descriptively. Any additional analyses will be performed separately and not form part of this SAP.

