### **1.3 Schedule of Activities**

The Schedule of Activities (SoA) at each visit for this study is provided in [Table 2](#). Details of the schedule of at-home and site visit patient-reported outcome (PRO) assessments are provided in [Table 3](#).

**Table 2** Schedule of Activities

Study period	Screening	Double-blind treatment period													OLE			IPD/ EOT c	FU (12 wks after last dose of IP)	UNS d	Details in CSP section
		V2	V3	V4	V5	V6	V7	V8	V9	V10	V11	V12	V13/ EOT a	Every 4 wks (V14 to V22) b	V19	Every 12 weeks (From V23)					
Visit	V1	0	2	4	6	8	12	16	20	24	28	32	36	40-72	60	From Week 76					
Week (Wk)																					
Visit window (days)	(Target 0-4 days)	±3	±3	±3	±3	±3	±3	±3	±3	±3	±3	±3	±3	±7	±7	±7	±7	±7			
General Procedures																					
Informed consent	X																				Appendix A 3
Demography/medical history	X																				Sections 5.1 and 5.2
Inclusion/exclusion criteria	X	X																			Sections 5.1 and 5.2
Record concomitant medications, including OCS dose and compliance check e	X	X	X	X	X	X	X	X	X	X	X	X	X	X	X	X	X	X	X	Section 6.5	
Randomization		X																			Section 6.3.1

**Table 2** Schedule of Activities

Study period	Screening	Double-blind treatment period													OLE			IPD/ EOT c	FU (12 wks after last dose of IP)	UNS d	Details in CSP section
Visit	V1	V2	V3	V4	V5	V6	V7	V8	V9	V10	V11	V12	V13/ EOT a	Every 4 wks (V14 to V22) b	V19	Every 12 weeks (From V23)					
Week (Wk)		0	2	4	6	8	12	16	20	24	28	32	36	40-72	60	From Week 76					
Visit window (days)	(Target 0-4 days)	±3	±3	±3	±3	±3	±3	±3	±3	±3	±3	±3	±3	±7	±7	±7	±7				
Disease Measurements																					
Disease state, BPDAL IGA, and CCI	X	X	X	X	X	X	X	X	X	X	X	X	X	CCI					Sections 8.1.1.1, 8.1.1.2, 8.1.1.3, and 8.1.1.4		
CCI								X						X	X e				Section 8.1.1.5		
		X												X					Section 8.1.1.6		
Healthcare resource utilization		X	X	X	X	X	X	X	X	X	X	X	X	X	X	X	X	X	Section 8.1.1.7		
PRO Procedures																					
Distribution of handheld device and instruction on use h		X																	Section 8.1.2		

**Table 2** Schedule of Activities

Study period	Screening	Double-blind treatment period													OLE			IPD/ EOT c	FU (12 wks after last dose of IP)	UNS d	Details in CSP section

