**Table 3** **Schedule of PRO Assessments**

Instruments	Schedule
Peak Pruritus Numeric Rating Scale and OCS Usage	First assessment at site at V2, then at home every evening (17:00-23:59) starting the day after V2 at home thereafter until V22 (Week 72). a
BPDAI-Pruritus, AB-QoL, EQ-5D-5L	At site at every visit up to V22 (Week 72), and then every 12 weeks thereafter. At site at unscheduled, IPD, and follow-up visits.

a Participants will complete BPDAI-pruritus, AB-QoL, and EQ-5D-5L onsite using the tablet. Some participants may be exempted from completing the at home PRO assessments on the handheld device (ie, Peak Pruritus Numeric Rating Scale and OCS Usage) upon agreement with the AstraZeneca physician.  
AB-QoL, Autoimmune Bullous Disease Quality of Life; BPDAI, bullous pemphigoid disease area index; EQ-5D-5L, European Quality of Life-5 Dimensions; IPD, investigational product discontinuation; OCS, oral corticosteroids; PRO, patient-reported outcomes; V, visit.

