## BP Relapse

In the event of a suspected BP relapse (see [Table 6](#) for definition), the participant should attend an unscheduled visit. A BPDAI evaluation will be conducted at the time of the relapse, or as soon as possible afterwards.

Investigators will be required to record details pertaining to each relapse event in the eCRF from baseline (Visit 2) until IPD visit/end of treatment and follow-up visit. Details should include the BPDAI activity and pruritus score and the required intervention(s), eg, OCS dose increase, the OCS dose at the time of relapse, addition of immunosuppressive therapy or requirement for hospitalization. Participants who require the addition of OCS after taper or an increase in the dose of OCS will be defined as having a relapse.

The management of participants who relapse will be according to standard of care. See [Section 6.5.1](#) for further details. The participant's relapse is managed with the addition of OCS and tapering should be recommended as soon as the relapse has been appropriately controlled as per current guidelines ([Feliciani et al 2015](#)). In case of a relapse during steroid tapering, the OCS dose may be increased to the previous dosage that symptoms were controlled. For recurrent relapses the OCS dosing regimen and tapering schedule will be at the Investigator's discretion. If the participant requires therapy other than OCS (eg, immunosuppressants), the study treatment may need to be discontinued but this should be discussed with the study physician prior to decision making. In the event that discontinuation of IP is required, the participant will still be asked to continue with the study assessments until the end of the double-blind period at Week 36. For relapse during OLE, the use of topical and/or oral corticosteroids and the schedule of taper will be at the discretion of the Investigator; however, it is recommended to follow the protocol taper schedule. The goal of therapy will be to taper off steroids to benralizumab monotherapy as soon as clinically indicated. In the event that the Investigator will need to control relapse with an immunosuppressant in the OLE, the participant will be withdrawn from the study and will not receive further benralizumab therapy. Participants may additionally be asked to allow future contact to provide follow-up clinical details regarding their health and information on disease state.

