#### **8.1.1.7 Healthcare Resource Utilization**

Broad-based all-cause and BP-related healthcare resource utilization information will be collected by the Investigator, or designee, in accordance with the SoA ([Table 2](#)) and recorded in the appropriate eCRF module. Protocol-mandated procedures, tests, and encounters are not included.

At randomization, retrospective all-cause and BP-related healthcare resource utilization information will be collected with a one-year recall period. At all subsequent visits, all-cause and BP-related healthcare resource utilization information will be collected with a recall period of ‘since last scheduled visit’.

The data collected may be used to conduct exploratory economic analyses and include:

- Number and duration of medical care encounters, including surgeries, and other selected procedures (inpatient and outpatient)
- Duration of hospitalization (total days or length of stay, including duration by wards [eg, intensive care unit])
- Outpatient medical encounters and interventions (including specialist visits, General Practitioner visits, home health care visits, and emergency room visits, etc.)
- Number and type of diagnostic and therapeutic tests and procedures

CCI

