#### **9.4.6.2 Healthcare Resource Utilization**

BP-related healthcare resource utilization assessments will be completed at the visits specified in the SoA ([Table 2](#)). The set of assessments will include the frequency and duration of hospitalization, and frequency of office visits and emergency room visits. These endpoints

will be summarized using descriptive statistics for each treatment group, and will include an annualized rate of hospitalizations due to BP and an average length of hospital stay due to BP. To support these summaries, a negative binomial regression model may also be fitted to each of these endpoints if deemed appropriate.

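### Healthcare resource use is asked about twice for the days before an unscheduled visit, because recall always runs back to the last scheduled visit and no rule removes duplicates

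*SAP*

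**What the plan says.** The protocol (8.1.1.7) sets a one-year look-back at randomization and then this rule: "At all subsequent visits, all-cause and BP-related healthcare resource utilization information will be collected with a recall period of ‘since last scheduled visit". SAP 3.6.6 repeats it for BP-related use and points to the Schedule of Activities for the visits: "At all subsequent visits (see CSP Table 2), BP-related healthcare resource utilization information", it says, "will be collected with a recall period of ‘since last scheduled visit". Neither document gives unscheduled visits a different window or restarts the window after one.

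In protocol Table 2, the row labelled "Healthcare resource utilization" is blank at screening and marked from Visit 2 onwards, apparently including the unscheduled column. The footnote to that column keeps its required assessments in force to Week 72. Under BP Relapse (protocol 8.1.1.1), when relapse is suspected "the participant should attend an unscheduled visit".

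On analysis, SAP 3.6.6 states: "All available data will be included, regardless of taking rescue medication or withdrawal from study". It plans descriptive summaries and gives no rule for an encounter reported at two visits. Protocol 9.4.6.2 adds frequencies of office and emergency visits, "an annualized rate of hospitalizations due to BP and an average length of hospital stay due to BP", and possibly a negative binomial model.

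**The concern.** A recall window that always begins at the last scheduled visit is sound if data are taken only at scheduled visits. Once they are also taken at an unscheduled visit, two consecutive collections share the same starting point. The days up to the unscheduled visit are covered by both, so a site following the instruction reports any encounter on those days twice.

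At stake are the exploratory 36-week counts of office visits, emergency visits, tests and procedures, and to a lesser degree the hospitalization rate and length of stay. Relapse is one stated reason for an unscheduled visit and is itself an efficacy outcome. If relapse visits are more common in one arm, that arm collects more duplicates, and an uncorrected comparison of healthcare use would be biased against it.

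**Working it through.** The documents give no figure for this overlap, so there is none to reproduce.

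**1. Are unscheduled visits included?** The columns after screening are Visits 2 to 13 (12), three open-label columns, IPD/EOT, follow-up and unscheduled: 18 in all. The table text available for this review, read from a PDF, shows 17 marks in the row, one short. The row for BPDAI-Pruritus, AB-QoL and EQ-5D-5L is also one short (18 marks for 19 columns), yet protocol Table 3 confirms that those instruments are completed "At site at unscheduled, IPD, and follow-up visits". The healthcare-use row has no blank at its end, and the text of both documents refers to all subsequent visits. The unscheduled mark is therefore well supported, but should be checked against the original table.

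**2. How the windows overlap.** Take scheduled visits on study days 141 (Week 20) and 169 (Week 24), an emergency visit on day 150 and a relapse visit on day 152. The relapse visit asks about days 141 to 152. The Week 24 visit asks about days 141 to 169. The day-150 encounter falls in both.

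**3. Expected overlap per unscheduled visit.** Scheduled visits are at Weeks 0, 2, 4, 6, 8, 12, 16, 20, 24, 28, 32 and 36, giving four intervals of 14 days and seven of 28 days: 56 + 196 = 252 days. For one unscheduled visit at a uniformly random time, the mean overlap within an interval of length L is L/2, and the chance of landing in that interval is L/252. So:

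- Expected overlap e = Σ(L²/2) / ΣL = [(4 × 196 + 7 × 784)/2] / 252 = 3136/252 = 12.4 days.
- Share of the period = 12.4/252 = 4.9%.
- Within a 4-week interval, the mean overlap is 14 days.

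**4. Effect on a comparison if nothing is de-duplicated (illustration).** Assumptions: one unscheduled visit per relapsing participant; relapse in 67% on placebo (from the 33% relapse-free on placebo in the mepolizumab trial cited in SAP 1.3) and 37% on benralizumab (assumed).

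*Encounters evenly spread.* Inflation = 1 + r × e/252, where r is the relapse proportion.

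- Placebo: 1 + 0.67 × 0.0494 = 1.033.
- Benralizumab: 1 + 0.37 × 0.0494 = 1.018.
- Factor on the rate ratio: 1.018/1.033 = 0.986.

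*Encounters m times as frequent as background in the days before the relapse visit.* Inflation = [252 + r(m − 1)e + r·m·e] / [252 + r(m − 1)e].

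| m | Placebo | Benralizumab | Factor on rate ratio |
|---|---|---|---|
| 1 | 1.033 | 1.018 | 0.986 |
| 3 | 1.093 | 1.053 | 0.963 |
| 5 | 1.146 | 1.085 | 0.947 |
| 10 | 1.255 | 1.157 | 0.922 |

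With even spread and relapse of 67% in both arms, both are inflated by 3.3% and the factor is 1.

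**5. With the window reset.** If recall starts at the last visit of either kind, no day is covered twice.

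**The case against.** The strongest reply is that asking twice is not counting twice. Data go into an eCRF module that is not shown, and nothing in either document says that visit-level tallies are added together. If the module is a dated log, a repeated encounter can be recognised and removed in routine programming. Hospitalizations are the clearest case: SAP 3.1.6 refers to their start and end dates, SAP 3.6.6 requires hospitalizations after consent to be reported as SAEs, and protocol 8.3.2 collects admission and discharge dates for SAEs. This stands, and limits the firm finding to double collection. It does not remove the point: no de-duplication rule is written, and the documents do not show that the other encounter types are dated.

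A second reply is that the link to relapse is loose. Relapse can be found at a scheduled visit, since disease state is assessed at each one. Unscheduled visits also occur for rescheduled doses, where vital signs are the stated minimum (protocol 6.1.2). Protocol-mandated encounters are excluded from the data, so the relapse visit itself need not count. This also stands, and makes any imbalance between arms conditional.

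A reader might go further and infer that relapse-related encounters are inflated by, say, 25% to 100%. The documents do not support that. Such a range comes from assuming one encounter per relapsing participant and a share q of encounters before the unscheduled visit; the inflation is then simply the assumed q, and background encounters are ignored.

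**Conclusion.** The recall rule, applied as written, collects the days between a scheduled visit and a following unscheduled visit twice: about 12.4 of 252 days (4.9%) per unscheduled visit, assuming uniform timing and that the Table 2 row includes the unscheduled column. Unless the eCRF or programming removes duplicates, undated counts of office and emergency visits, tests and procedures would be inflated. Hospitalizations are less exposed.

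It may be tempting to conclude that the plan builds in a bias in favour of benralizumab. That requires both that duplicates survive into the tables and that relapse visits really differ between arms; the documents establish neither. Under the assumed 67% versus 37%, the distortion is a factor of about 0.99 with evenly spread encounters and 0.96 to 0.92 with 3- to 10-fold clustering. With equal relapse rates the ratio is not distorted.

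The endpoint is exploratory, summarized descriptively and outside the testing hierarchy, so the primary and key secondary results are untouched. This is a low-priority correction, worth making because it is nearly free.

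**What to change.** In protocol 8.1.1.7, SAP 3.6.6 and the eCRF instruction, define recall as running since the last visit at which healthcare resource utilization was collected, whether scheduled or unscheduled.

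For data already collected, add to SAP 3.6.6, before unblinding, that each encounter is counted once:

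- Where encounters are dated, match on type and date, and cross-check hospitalizations against SAE admission and discharge dates.
- Where only counts exist, use the scheduled-visit record alone when a later scheduled visit covers the same window.

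Fixing the rule before unblinding means it is not chosen with knowledge of the arms. Confirm the unscheduled mark in the original Table 2 at the same time. The cost is one phrase in the protocol and eCRF instruction, and one programming step.

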3.6.7 Biomarkers

3.6.7.1 Serum and plasma biomarkers

[figure not shown]
Serum and plasma samples will be collected according to the CSP Table 2 to evaluate the pharmacology of benralizumab as well as biomarkers of eosinophil recruitment, activation, and survival (eg, absolute eosinophil count, IL-5, EDN, eotaxin).

Additional markers of cellular inflammation and/or activation may be assessed including, but not limited to, those associated with humoral autoimmunity (total serum IgE, IgG directed against auto-antigens BP-180 and/or BP-230), T cell subsets (eg, IL-13, IFN-gamma, IL-17), eosinophil granule proteins (eg, MBP, eosinophil peroxidase), epithelial cell damage (eg, TSLP, IL-25, IL-33), itch (IL-31), and pain (substance P). The results from such studies will not be reported in the CSR but in separate reports or publications as appropriate. The corresponding analyses are not covered in this SAP.

3.6.7.2 Tissue histology and immunostaining

Skin histology and immunohistochemistry data will be analysed separately and not form part of this SAP.

[figure not shown]
CCI

3.6.9 OLE

The effect of benralizumab will be explored in participants in the OLE period by assessing

CCI

[figure not shown]
Peak Pruritus NRS at each visit up to Week 72

AB-QoL at each visit up to Week 72

EQ-5D-5L at each visit up to Week 72

These endpoints will be derived in the OLE period using the same rules, assumptions and intercurrent events applied for the double-blind period analysis.

CCI

4 ANALYSIS METHODS

4.1 General principles

The primary analysis will be based on the initial 36-week, double-blind, placebo-controlled phase of the study, and will compare all participants randomized to benralizumab until Week 36 against all participants randomized to placebo until Week 36.

All personnel involved in the analyses of the study will remain blinded until the primary DBL and protocol deviations are identified.

The current SAP focuses on the double-blind study period with a high-level description of the descriptive analysis for the OLE analysis. If required, additional detail regarding descriptive analyses in the OLE period will be provided in a separate OLE SAP.

The primary CSR will focus on data from the double-blind period as defined in Section [3.1.2](#).
Final data collected during the OLE period will be reported separately.

Efficacy endpoints will be analysed using the FAS, the analysis of safety endpoints will be based on the safety analysis set. Analysis sets are defined in Section [2.1](#).

Summary data will be presented in tabular format by treatment group. Categorical data will be summarized using frequency and percentages, where the denominator for calculation is the underlying analysis set population unless otherwise stated. Continuous data will be summarized with descriptive statistics of number of available observations, mean, standard deviation, median, minimum and maximum, and quartiles where more appropriate. Data listings will be sorted by treatment and participant number.

All point estimates will be presented together with 95% confidence intervals (CIs) as measures of precision and nominal 2-sided p-values, rounded to 4 decimal places.

Hypothesis testing for the primary and key secondary endpoints will be based on a 2-sided test and carried out using a 5% significance level. If a p-value is less than 0.05, the treatment effect favours benralizumab and the decision will be to reject the null hypothesis (H0) and the alternative hypothesis (H1) will be accepted, subject to the testing strategy outlined in Section [4.1.1](#) below. Any p-values presented for endpoints other than those included in the testing strategy will be nominal (i.e. not multiplicity adjusted).

All analyses for the OLE endpoints will be descriptive, as no placebo-control data will be available for this period. Consequently, no hypothesis testing will be performed.

Sensitivity analyses will be explored to assess the robustness of treatment effects for the primary and key secondary endpoints. Different missing data mechanisms (eg, values missing at random and values missing not at random) and tipping point analyses will be considered to assess the robustness of the treatment effect for these endpoints. The use of multiple imputation approaches will be considered. Full details are reported in Appendix [8.1](#).

The data analyses will be conducted using the SAS® System (SAS Institute Inc., Cary, NC). All SAS® programs used to generate analytical results will be developed and validated according to AstraZeneca SAS® programming standards and validation procedures.

Table 8 Primary and key secondary efficacy and main safety estimands

Statistical category	Treatment condition	Endpoint (Population)	Intercurrent event strategy	Population level summary (Analysis)	
Primary Objective: To compare the clinical efficacy of benralizumab with placebo in participants with symptomatic BP					
Primary	Treatment with benralizumab versus placebo, regardless of IP compliance; restricted medication use indicates treatment failure	Proportion of participants who are in complete remission while off OCS for ≥ 2 months at Week 36 (FAS)	
 • Treatment discontinuation – treatment policy • Rescue with OCS^a – treatment policy • Restricted medication use – composite (non-responder) • Study withdrawal – composite (non-responder) 	Odds ratio and difference in proportion of participants who are responders at Week 36 (logistic regression model)	4.2.6.1
Secondary Objective: To compare the effect of benralizumab with placebo on supportive measures of clinical efficacy in participants with symptomatic BP up to Week 36/up to Week 16					
Key secondary	Treatment with benralizumab versus placebo, regardless of IP compliance; rescue with OCS and restricted medication use indicate treatment failure	Proportion of participants who remain relapse-free up to Week 36 (FAS)	
 • Treatment discontinuation – treatment policy • Rescue with OCS^a – composite (not relapse free) • Restricted medication use – composite (not relapse free) • Study withdrawal – composite (not relapse free) 	Odds ratio and difference in proportion of participants remaining relapse free up to Week 36 (logistic regression model)	4.2.7.1
	Treatment with benralizumab versus placebo, regardless of IP compliance	Cumulative OCS exposure (mg/kg) from baseline to Week 36 and from baseline to Week 16 (FAS)	
 • Treatment discontinuation – treatment policy • Restricted medication use – effectiveness (includes OCS dosing up to occurrence of event) • Study withdrawal – effectiveness (includes OCS dosing up to occurrence of event) 	Difference in mean cumulative OCS exposure (mg/kg) from baseline to Week 36 and from baseline to Week 16 (MMRM)	4.2.7.2

	Treatment with benralizumab versus placebo, regardless of IP compliance; rescue with OCS and restricted medication use indicate treatment failure	Change from baseline in BPDAI activity score at Week 36 (FAS), change from baseline in BPDAI-Pruritus score at Week 36 (FAS)	
 • Treatment discontinuation – treatment policy • Rescue with OCS^a – composite (LOCF) • Restricted medication use – composite (LOCF) • Study withdrawal – hypothetical (multiple imputation) 	Difference in mean change from baseline in BPDAI activity score/BPDAI-Pruritus score at Week 36 (ANCOVA)	4.2.7.3/ 4.2.7.4
Safety Objective: To compare the safety and tolerability of benralizumab with placebo in participants with symptomatic BP					
Safety	Treatment with benralizumab versus placebo, regardless of restricted medications.	
 • AEs • SAEs • Vital Signs • Physical examination (Safety) 	
 • Remained adherent to intervention (on-treatment) 	
 • Descriptive 	4.2.9

^a Rescue with OCS is defined as needing to increase OCS dose after previously having achieved disease control.

ANCOVA, analysis of covariance; BP, bullous pemphigoid; BPDAI, bullous pemphigoid disease area index; FAS, full analysis set; IP, investigational product; LOCF, last observation carried forwards; MMRM, mixed-effect model for repeated measures; OCS, oral corticosteroids.

